Protocol Title	Phase III, randomized, group, study of AB103 a necrotizing soft tissue in ACCUTE (AB103 Clini Necrotizing Soft Tissue	double-blind, placebo-controlled, parallel- as compared to placebo in patients with ifections (NSTI) cal Composite Endpoint Study in Infections)
Location(s)	A multicenter study, that qualified participating sit	will be conducted in approximately 75 es in the US and France
Phase of Development	Phase 3	
Study population	Patients clinically diagno (NSTI) who are schedule their standard of care (So subsequently have a surg	sed with necrotizing soft tissue infections d for an urgent surgical intervention as part of C) for the treatment of their infection and who ically confirmed diagnosis of NSTI.
Study Objectives	 Primary objective: To demonstrate the efficacy of AB103 as compared to placebo, in patients diagnosed with NSTI, using a clinical composite success endpoint: The NSTI clinical composite score, NICCE (Necrotizing Infections Clinical Composite Endpoint) will be defined as the primary end point which will be composed of the following patient outcomes (i) Alive at Day 28, (ii) Day 14 debridements ≤3 (iii) No amputation done after the first debridement (iv) Day 14 modified SOFA (mSOFA) score ≤1 (mSOFA includes respiratory, cardiovascular, central nervous system (CNS), renal, and hematologic organ components but not hepatic/liver component) (v) Reduction of ≥3 score points between Baseline and Day 28, COFA 	
	Component	NICCE
	Survival	Alive at Day 28
	Local component	 ≤3 debridements throughout Day 14 No amputation beyond first debridement
	Systemic component	 mSOFA score of ≤1 at Day 14 Reduction of ≥3 score points between Baseline and Day 14 mSOFA score
	To be considered a succe NICCE. A two-sided $\alpha=0$ relative to placebo for the	ss, patients must meet all components of the 0.01 will be used to test superiority of AB103 e primary endpoint (NICCE).

Conditional co-primary end point:
To demonstrate the efficacy of AB103 as compared to placebo, in patients diagnosed with NSTI, using a modified clinical composite success endpoint that includes (i) Alive at Day 28, (ii) Day 14 debridements \leq 3 (iii) No amputation done after the first debridement. To be considered a success, patients must meet all 3 components of this modified composite endpoint.
The conditional co-primary end point will only be tested if superiority is demonstrated for the primary endpoint at a two-sided α =0.01 significance level in order to account for multiple comparisons. A two- sided α =0.05 will be used to test superiority of AB103 relative to placebo for the co-primary endpoint.
Secondary objectives:
• To demonstrate the safety of AB103 when administered as a single dose of 0.50 mg/kg to patients diagnosed with NSTI
 To demonstrate the efficacy of AB103 as compared to placebo, in patients diagnosed with NSTI, using the 5 component clinical composite endpoint but with mSOFA ≤1 at Days 21 and 28
 Comparison of the distribution of mSOFA scores between treatment groups at Days 14 and 21
• Kaplan-Meier analysis of the time to resolution of mSOFA score to ≤ 1 with censoring at Day 14
 related to the individual components of the NICCE in patients with NSTI
 To demonstrate efficacy of AB103 in relation to the critical care and hospital stay parameters: a. Intensive care unit (ICU) days b. ICU-free days c. Days on ventilator d. Ventilator free days e. Vasopressor days f. Vasopressor free days a. Vasopressor free days
 o To demonstrate the efficacy of AB103 in patients with septic shock.
• To determine the incidence of Stage 2 and 3 acute kidney injury (AKI) (using the KDIGO criteria) and compare the rates of complete recovery by Day 28 between the AB103 treated patients and the placebo treated patients.
 Additional AKI endpoints: To determine the incidence of Stage 2 and 3 AKI (using the KDIGO criteria) and compare the rates of complete and partial recovery by Day 28 between AB103 and placebo treated patients Determine the incidence of Stage 1, 2 and 3 AKI and compare the rates of complete recovery between the
 AB103 and placebo treated patients Determine the incidence of Stage 1, 2 and 3 AKI and compare the rates of complete and partial recovery between the AB103 and placebo treated patients

	 Calculate time to complete recovery from AKI 		
	 Calculate time to partial recovery from AKI 		
	 To demonstrate the safety of AB103 in regard to secondary 		
	infections		
	Exploratory objectives:		
	• To conduct an exploratory evaluation of the clinical response		
	by baseline pathogen		
	• 10 evaluate microbiological outcome in the microbiological		
	 To conduct an exploratory evaluation of plasma and urinary 		
	biomarkers in patients with AKI		
	• To conduct an exploratory evaluation of blood leukocyte		
	transcriptome (RNA expression) profiling in patients with		
	AB103 versus placebo		
	• To evaluate health economic and financial outcomes		
	associated with the treatment		
	• To evaluate NICCE outcome in screen failure patients with has line $mSOEA = 2$ and next an article $mSOEA > 2$. Note:		
	baseline mSOFA = 2 and post-operative mSOFA \geq 5. Note: These patients will not be included in the modified Intent-to-		
	Treat (mITT) population analysis (they will not receive		
	blinded study drug) and only considered to be an observational		
	cohort		
	• To evaluate the immunogenicity of Reltecimod (formerly		
	AB105)		
Study Hypothesis	The primary hypothesis of this study is that in addition to SoC, AB103 will demonstrate a clinically significant treatment benefit over placebo.		
	This hypothesis will be addressed by measuring the effect of AB103 on a composite of clinical parameters associated with the disease course of		
	patients with NSTI, using a responder analysis. A responding patient		
	must meet an 5 parameters of the composite clinical success end po while a non-responding patient can fail by not meeting any one of t		
	parameters. These analyses are designed to demonstrate that in addition		
	to being safe, one dose of 0.5 mg/kg of AB103 will:		
	Improve systemic signs of the infection by improving organ function of patients compared to placebo as measured by:		
	Survival at Day 28		
	• mSOFA score on Day 14 and change from baseline to Day 14		
	\geq 3. A Day 14 mSOFA score of \leq 1 and a change from baseline		
	(pre-treatment) to Day $14 \ge 3$ will be required for a patient to		
	achieve the primary composite clinical success endpoint		
	Improve the local signs of the infection, as measured by:		
	• Reduced number of debridements, counted to Day 14. No more than 3 debridements to Day 14 will be required for a patient to achieve composite clinical success		
	• No amputation after the first debridement (amputation on the		
	first debridement is not considered a failure). A patient will be required to have had no amputations done after the first		

	surgical procedure in order to achieve composite clinical success.
Number of Patients:	290 patients will be recruited into the study and randomized to receive either 0.5 mg/kg AB103 or placebo in a 1:1 ratio. Randomization will be stratified within center by the diagnosis of Fournier's Gangrene and mSOFA score category (3-4 vs >4) at screening. The study will be conducted with interim analyses for futility at 100 patients.
Inclusion Criteria:	 Age: ≥12 years Surgical confirmation of NSTI by attending surgeon (e.g. presence of necrotic tissue, thrombosed vessels in the subcutaneous tissue, lack of bleeding and "dishwater" (cloudy, thin, gray) fluid) due to presumed bacterial infection (necrotizing cellulitis (most commonly group A strep), necrotizing fasciitis, necrotizing myositis and myonecrosis, NSTI of the perineum, bacterial synergistic gangrene. Clostridial gas gangrene) that may be supported by specific signs and symptoms (e.g. tense edema outside area of compromised skin, pain disproportionate to appearance, skin discoloration, ecchymosis, blisters/bullae, necrosis, tense edema, crepitus and/or subcutaneous gas). Patients with NSTI following intra-abdominal operation are eligible if adequate source control of intra-abdominal process has been established mSOFA score ≥3 (in any one or combination of the 5 major components of SOFA score with any one organ component having a score of at least 2: cardiovascular, respiratory, renal, coagulation, CNS), measured as close as possible to the first debridement, (but before first debridement is performed). IV drug administration within 6 hours from the clinical diagnosis and the decision at the study site, to have an urgent surgical exploration and debridement (drug should not be administered until surgical confirmation is established). If a woman is of childbearing potential, she must consistently use an acceptable method of contraception from baseline through Day 28. Acceptable birth control methods include oral contraceptive medication, an intrauterine device (IUD), an injectable contraceptive (such as Depo-Provera®), a birth control patch, a barrier method (such as condom or diaphragm with spermicide) or abstinence. Non-childbearing potential is defined as current tubal ligation, hysterectomy, or ovariectomy or postmenopause (1 year without menses with an appropriate clinical profile at the appropriate age e.g.

Exclusion Criteria: 1. BMI > 51;	
2. Patient who has been operated at least once for	the current
NSTI infection and had a curative deep tissue d	ebridement
(patients who underwent prior diagnostic minor	surgery are
allowed to enter into the study);	n the involved
area - associated with ischemic wounds/ulcers	or gangrene, and
/or other significant symptoms of inadequate va	scular supply or
where limb amputation is considered likely with	hin 7 days due
to the peripheral vascular disease;	
4. Diabetic patients with peripheral vascular disea	se who present
with below the ankle infection;	
5. Patient with burn wounds; 6. Current condition of: (a) Inability to maintain a	mean arterial
pressure > 50 mmHg and/or systolic blood pressure	sure > 70
mmHg for at least 1 hour prior to screening des	pite the
presence of vasopressors and IV fluids or (b) a	patient with
respiratory failure such that an SaO ₂ of 80% can	nnot be achieved
or (c) a patient with refractory coagulopathy (IN	NR > 5) or
thrombocytopenia (platelet count <20,000) that	does not
blood products	
7. Chronic neurological impairment that leads to a	neuro mSOFA
component ≥ 2	
8. Recent cerebrovascular accident in the last 3 m	onths.
9. Patients with cardiac arrest requiring cardiopul	nonary
resuscitation within the past 30 days;	dave of study
due to underlying medical condition such as pe	orly controlled
neoplasm (e.g. Stage III or IV cancer);	ing controlled
11. Patient or patient's family are not committed to	aggressive
management of the patient's condition, or the co	ombination of
necrotizing skin infection and underlying illnes	s makes it
unlikely that life support will be maintained;	aninian of the
I2. Any concurrent medical condition, which in the	nation of the
objectives of the study or the patient will not be	enefit from
treatment such as:	
 CHF {NYHA class III-IV} 	
• Severe COPD {GOLD stage III-IV. or	chronic
hypoxemia (PaO ₂ <55 mmHg) on room	air, or chronic
use of home ventilation, or unable to cl	imb stairs or
perform household duties due to chroni disease resulting in severe everyise rest	c obstructive
continuous home oxygen prior to hospi	tal admission
(sleep apnoea treated with continuous r	ositive airway
pressure or biphasic positive airway pre	essure oxygen
during sleep is acceptable)}	
 Liver dysfunction {Childs-Pugh class C 	C}
 Immunosuppression (see Appendix F, S 	Section 15.6 for
list of excluded immunosuppressive me	edications)
• Neutropenia < 1,000 cells/mm ⁻ not due	to the

	 Receiving or about to receive chemotherapy or biologic anti-cancer treatment although hormonal manipulation therapies for breast and prostate malignancies are permitted Hematological and lymphatic malignancies in the last 5 years Known HIV infection with CD4 count < 200 cells/mm3 or < 14% of all lymphocytes; Patients with known chronic kidney disease (documented pre-illness creatinine value(s) ≥2.0) or patients receiving renal replacement therapy for chronic kidney disease: either hemodialysis, peritoneal dialysis, hemofiltration such as Continuous Veno-Venous Hemofiltration (CVVH) or hemodiafiltration Patients that are treated with continuous hemofiltration (e.g. Continuous Veno-Venous Hemofiltration) for acute kidney dysfunction, not due to NSTI, starting prior to study drug administration.
	Exception: Patients with acute kidney dysfunction due to NSTI may be enrolled in the event that the patient is off the treatment from time of study drug administration and up to at least one hour post study drug administration.
	 16. Pregnant or lactating women; Women of childbearing potential must have a negative β-subunit hCG pregnancy test immediately prior to study entry 17. Previous enrollment in a clinical trial involving investigational drug or a medical device within 30 days before provision of written informed consent for the study or within five half-lives of the investigational drug, whichever is longer. 18. Previous enrollment in this protocol, ATB-202, or the Phase 2 NSTI trial of AB103, ATB-201, or the current Phase 2 SA-AKI trial of AB103, ATB-203.
Investigational Product: type, dose and mode of	AB103 is the sodium acetate salt of a 10 amino acids synthetic peptide that is homologous to specific amino acid residues of the T-lymphocyte receptor CD28.
auministration	AB103 will be supplied in glass vials as a lyophilized powder to be reconstituted with sterile water for injection (WFI). Drug will be reconstituted on the day of its administration, in close proximity to infusion time, and several vials will be pooled together to compose the requested dose. Final volume for infusion will be calculated based on the patient's weight plus adequate priming volume of the IV line.
	Drug will be administered as an intravenous infusion, separate from other medications, over 10 minutes using a syringe pump (may be manually pushed if approved by the medical monitor). Volume of administration will be dependent on patients' actual weight.
	The dose of AB103 will be 0.50 mg/kg, administered as a one-time dose, either during the first surgery or immediately after the first surgery, all within the 6 hour time-window from clinical diagnosis and decision for urgent surgical exploration and debridement (study drug should only be administered after NSTI diagnosis is confirmed surgically). Blinded placebo will be sterile normal saline (0.9%)

This is a randomized, double-blind, placebo-controlled, parallel-group, multicenter study, to evaluate the efficacy and safety of a single dose of AB103 versus placebo (both in addition to SoC). Screening starts upon notification of study team about a patient with possible NSTI and lasts until study drug administration. Screened patients meeting inclusion/exclusion criteria and able to provide written informed consent (legal patient representative consent acceptable) may be randomized to one of 2 treatment arms (AB103 or placebo) in a 1:1 ratio. Treatment regimen consists of a single dose of 0.50 mg/kg AB103 or placebo, each administered as a single intravenous infusion over 10 minutes.

Study drug administration may take place during or after the surgical exploration and debridement, but no later than 6 hours from clinical diagnosis of NSTI and a decision at the study site for urgent surgical wound exploration and debridement.

All patients will receive SoC antimicrobial treatment and any other SoC treatment, as determined by the Investigator

SOFA score definition:

Screening mSOFA:

Screening mSOFA score components are to be captured and the total score to be calculated prospectively and must be performed prior to first debridement: The screening mSOFA score should be evaluated any time after arrival at the hospital (may include referring hospital), although no more than 6 hours prior to anticipated first debridement. Screening mSOFA score must be \geq 3, with one organ component having a score of at least 2, to be considered eligible for enrollment. Sites are encouraged to re-evaluate mSOFA score as close to surgery as feasible for patients not meeting mSOFA \geq 3 inclusion criteria during initial screening. Screening mSOFA will include measurements of the score components in the following organ/systems: respiratory (to include evaluation of oxygenation either directly by arterial blood gas test or by calculation of PaO₂ from SpO₂, in case it is not possible to obtain arterial blood to determine the SOFA respiratory parameter), cardiovascular, renal, coagulation and CNS.

mSOFA score: measurements of a 5 organ systems, including CNS. To be measured on days 1, 2, 3, 7, 10, 14, 21 and 28 and calculated retrospectively.

mSOFA respiratory parameter:

In case it is not possible to take arterial blood gases to determine the SOFA respiratory parameter, SpO2/FiO2 ratio can be imputed for PaO2/FiO2 ratio.

-

Outcome measures	Primary Efficacy Measure:						
	 NICCE: Clinical composite success end point: Success is defined as meeting all 5 components of the composite score: Alive until Day 28, (ii) Day 14 debridements ≤3 (iii) No amputation done after the first debridement (iv) Day 14 mSOFA score ≤1 (v) Reduction of ≥3 score points between Baseline and Day 14 mSOFA score. 						
	Conditional Co-Primary Efficacy Measure:						
	 Modified clinical composite endpoint: Success is defined as meeting all 3 components of the composite score: Alive until Day 28, (ii) Day 14 debridements ≤3 (iii) No amputation done after the first debridement 						
	Safety Measures:						
	 Measures throughout Day 28: AEs (includes Serious Adverse Events (SAEs)), clinical safety laboratory (through Day 14), secondary infections, determination of survival through Day 28. 						
	Other measures: physical exam, vital signs, ECG (days 0 and 1); (specific times of these parameters are described in the table of study visits and procedures below)						
	Secondary Measures:						
	 5 component clinical composite endpoint but with mSOFA ≤1 at Days 21 and 28 						
	• Distribution of mSOFA scores at Days 14 and 21						
	• Kaplan-Meier analysis of the time to resolution of mSOFA score to ≤ 1 with censoring at Day 14						
	• Single components of the composite endpoint :						
	 Alive at Day 28 Number of patients with debridements by Day 14 ≤3 Number of amputations (excision to a joint space) (done after first debridement) mSOFA score on Day 14 ≤1 Reduction of ≥3 score points between Baseline and Day 14 						
	 Critical care and hospital stay parameters, to be measured until Day 28: 						
	• ICU-free days						
	 Days in ICU Days on ventilator 						
	• Ventilator free days						
	 Vasopressors days/ Vasopressors free days Hospital length of stay (days) 						
	Clinical local parameters:						
	 Number of debridement to days 7, 10, 14 and 28 Proportion of patients needing (up to Day 14): 						
	 only one debridement to control the infection ≥2 debridements to control the infection ≥3 debridements to control the infection 						
	 Clinical systemic parameters: Evaluation of organ function over time, using SOFA score Recovery from AKI 						
	Exploratory Measures:						
	• Evaluation of clinical response by baseline pathogen type						

Health economic information	 Evaluation of microbiological outcome in the microbiological evaluable population Correlation of plasma and urinary biomarkers with incidence of AKI, AKI staging and recovery from AKI Evaluation of blood leukocyte transcriptome (RNA expression) profiling in patients with NSTI and compare genomic profile in patients treated with AB103 versus placebo Evaluation of NICCE outcome in screen failure patients with baseline mSOFA = 2 and post-operative mSOFA ≥ 3 To evaluate the immunogenicity of Reltecimod (formerly AB103) Details of health economic information will be collected throughout the hospital course and post hospital discharge. The health economic information will include several parameters: Hospital length of stay (includes both ICU
	and hospital ward stay), length of ICU stay, days on the ventilator, number of surgical operations, hospital readmission information, and mSOFA scores.
Duration of study	Overall, the study is expected to last approximately 48 months (from first patient in to last patient out).

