15.3 Appendix C - modified SOFA

Value	0	1	2	3	4
Respiratory PaO ₂ /FiO ₂ ¹	>400	≤400	≤300	≤200 with respiratory support	≤100 with respiratory support
Coagulation Platelets	>150	≤150	≤100	≤50	≤20
Cardiovascular ²	No hypo- tension	MAP <70	Dopa ≤5 PE <100	Dopa > 5 Epi ≤ 0.1 NE ≤ 0.1 PE 100- 300	Dopa>15 Epi>0.1 NE>0.1 PE>300 VP>0.01
Neuro GCS	15	13-14	10-12	6-9	<6
Serum Creatinine OR Urine Output	<1.2	1.2-1.9	2.0-3.4	3.5-4.9 <500cc/ day	≥5.0 <200cc/ day

1. For patients on supplemental oxygen via nasal cannula, nasopharyngeal catheter or mask and for converting SpO2 values to PaO2 use the attached oxygen conversion tables.

2. Doses of dopamine (Dopa), epinephrine (Epi), norepinephrine (NE) are in micrograms/kg/min; phenylephrine (PE) is micrograms/min; vasopressin (VP) is U/min. Vasopressors must have been administered for at least one hour.

Oxygen Conversion tables

Estimating Pa02 from a given Sp02

SpO2 (%)	PaO2 (mmHg)
80	44
81	45
82	46
83	47
84	49
85	50
86	52
87	53
88	55
89	57
90	60
91	62
92	65
93	69
94	73
95	79
96	86
97	96
98	112
99	145

Estimating Fi02

Method	O2 flow	Estimated FiO2 (%)
Nasal cannula	1	24
	2	27
	3	30
	4	33
	5	36
	6	40
Nasopharyngeal catheter	4	40
	5	50
	6	60
Face mask	5	40
	6-7	50
	7-8	60
Face mask with reservoir	6	60
	7	70
	8	80
	9	90
	10	95

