3.5.4 Sequential Organ Failure Assessment (SOFA) Score

A modified version of the SOFA score will be used as a clinical end point and will be calculated as described in Section 5.2 and Appendix 5. The modification is that the liver component is not used. Individual parameters of the SOFA score will be collected as summarized as well as the modified SOFA total score (mSOFA). Data will be recorded in the CRF at specified time points according to the time and events schedule. Additionally, SOFA will be computed and described for screening, Day 7, and Day 14. Additional handling of the neuro deficit component is described below.

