4.6 Exploratory Subgroup Analysis

Exploratory subgroup analysis will be performed. For these exploratory analyses, primary efficacy, selected secondary efficacy, selected safety tables will be repeated stratified according to the following classifications:

- 1. Age \geq 65 years vs. \leq 65 years
- 2. Gender
- 3. BMI (<30 versus 30-<40 vs. ≥ 40 kg/m²),
- 4. White vs. non-white
- 5. AKI Status (Any AKI, Stage 2/3 AKI, non-AKI).
- 6. Patients Achieving Freedom from Durable Loss of Renal Function vs. not (among patients presenting with Stage 2 or Stage 3 AKI)
- 7. Presence of cardiovascular organ failure (SOFA component >=3 at baseline) vs. those without CV organ failure (except SOFA related tables)
- 8. Presence of respiratory organ failure (SOFA component >=3) at baseline vs. those without (except SOFA related tables)
- 9. LRINEC ≥ median vs. LRINEC < median
- 10. ANAYA ≥ median vs. ANAYA < median
- 11. APACHE II ≥ 10 vs. APACHE < 10
- 12. Type of bacteria (Gram-positive vs. Gram-negative and possibly a 'mixed' type if needed), list to be provided by Sponsor and other prevalent pathogens.
- 13. Prevalent sub types and classes of identified pathogens
- 14. Bacteremic vs. non-bacteremic (blood culture)

The results for any subgroup analysis will not be interpreted if there are fewer than five patients in either treatment group within that subgroup analysis.

The following tables will be provided for stratifications 1 through 11 listed above. These tables are described in more detail below. Only the primary endpoint table (Table 14.2.1.1) will be stratified for the subgroups 12, 13, and 14.

14.2.1.1	Comparisons of the Percentages of Patients Achieving Primary Composite Clinical Success Endpoint (NICCE) and its Components mITT Analysis Set†
14.2.1.2	Comparisons of the Percentages of Patients Achieving Conditional Co-Primary Endpoint (CCPE) and its Components mITT Analysis Set†
14.2.2.2	Modified SOFA Total Score and Organ Specific Scores Over Time to Day 14 Last Observation Carried Forward (LOCF) mITT Analysis Set†
14.2.2.4	Modified SOFA Total Score and Organ Specific Scores Over Time to Day 14 Change from Day 0 (Screening) - Last Observation Carried Forward (LOCF) mITT Analysis Set†
14.2.2.6	Modified SOFA Total Score and Organ Specific Scores Over Time to Day 14 Change from Day 1 - Last Observation Carried Forward (LOCF) mITT Analysis Set†
14.2.4.1	Critical Care and Hospital Stay Parameters Over Days 1 to 28 By Treatment Group mITT Analysis Set†

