5.1 Baseline Comparisons

Demographic and baseline characteristics will be summarized for each analysis set overall and by treatment group. Categorical variables including race, ethnicity, and gender will be summarized by counts and percentages. Continuous variables will be summarized using mean, median, standard deviation (SD), and minimum and maximum values. Continuous variables evaluated will include age, BMI, height, weight, systolic BP, diastolic BP, MAP, heart rate, and temperature; as well as ANAYA, LRINEC, and APACHE II scores. Presence of baseline sepsis will be summarized according to the numbers and percentages of patients with baseline cardiovascular and respiratory organ failure as reflected in screening component SOFA scores of 3 or 4. In addition presence of any AKI at baseline algorithmically determined, Stage 2/3 AKI at screening, and maximal AKI Stage 2/3 as assigned by the blinded adjudication panel will be summarized.

Analyses will be performed to confirm that the randomization resulted in no clinically significant group differences at baseline. Although emphasis will be on clinical significance, baseline comparisons will include t-tests or Wilcoxon rank-sum tests as appropriate for interval variables and chi-square or Fisher's exact tests as appropriate for nominal variables to aid in the screening for baseline differences. If there are clinically important baseline differences, multiple logistic regression will be used in supporting analyses to assess the impact of the imbalance on significance levels.

5.2 mSOFA

The Sequential Organ Failure Assessment score or SOFA was originally developed to track a patient's status during a stay in an intensive care unit (ICU)⁸,⁹. Each of six organ systems are evaluated (see Appendix 5) with ordinal scores 0 to 4. A total score is the sum of the component scores. For this study, the liver component is excluded and the resulting sum score is referred to in this study as 'mSOFA'.

Several approaches will be taken to summarize changes over time and between treatment groups in the clinical scores as described below.

mSOFA scores will be assessed as 1) observed cases, 2) last observation carried forward (LOCF), 3) using MMRM, and 4) categorized and combined with mortality and local activity as part of the primary composite clinical success endpoint, NICCE.

The following will be defined as OBSERVED mSOFA.

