SOFA – Sequential Organ Failure Assessment score

Can range from 0 -24

Respiratory system:

PaO ₂ / FiO ₂ (mmHg)	SOFA score
=>400	0
< 400	1
< 300	2
< 200 and mechanically ventilated	3
< 100 and mechanically ventilated	4

Nervous System:

Glasgow Coma Scale	SOFA score
15	0
13-14	1
10-12	2
6-9	3
< 6	4

Cardiovascular System

Mean Arterial Pressure (MAP) OR administration of vasopressors (mcg/Kg/minute)	SOFA score
$MAP \Rightarrow 70 \text{ mmHg}$	0
MAP < 70 mmHg	1
Dopamine <= 5 OR Dobutamine any dose	2
Dopamine > 5 <=15 OR epinephrine <=0.1 OR norepinephrine <= 0.1	3
Dopamine > 15 OR epinephrine > 0.1 OR norepinephrine > 0.1	4

MAP= (Systolic pressure + (2*Diastolic pressure))/3

Liver:

Bilirubin (mg/dl)	SOFA score
<1.2	0
1.2-1.9	1
2.0-5.9	2
6.0-11.9	3
>= 12.0	4

Coagulation:

Platelets x 10 ³ /mcl	SOFA score
=>150	0
< 150	1
< 100	2
< 50	3
< 20	4

Renal System:

Creatinine (mg/dl) (or urine output)	SOFA score
<1.2	0
1.2 - 1.9	1
2.0 - 3.4	2
3.5 - 4.9 (or < 500 ml/day)	3
>=5.0 (or < 200 ml/day)	4

Anaya score

Can range from 0 - 12

Variable on admission	Points
Heart Rate > 110 beats per minute	1
Temperature < 36.0 °C	1
Serum Creatinine > 1.5 mg/dl	1
Age > 50	3
White blood cells count > 40,000/mcl	3
Hematocrit > 50%	3

LRINEC – Laboratory Risk Indicator for Necrotizing Fasciitis

Can range from 0 - 13

	П
Variable, Units	Score
C-Reactive Protein mg/L	
< 150	0
>= 150	4
Total White Blood cells count per mm ³	
< 15	0
15 - 25	1
>25	2
Hemoglobin g/dL	
>13.5	0
11.0 – 13.5	1
< 11	2
Sodium mmol/L or meq/L	
>= 135	0
< 135	2
Creatinine µmol/L (mg/dL)	
<= 141 (1.595)	0
>141 (1.595)	2
Glucose mmol/L (mg/dL)	
<=10 (180.18)	0
>10 (180.18)	1

16 Appendix 6: Randomization Program: SAS call to R program

```
proc format;
value treatment fmt
  1 = 'Placebo'
  2 = 'Active'
run;
proc iml;
submit / R;
library(doParallel)
site hold <- seq(10, 49, by = 1)
strata hold <- c(1,2,3,4)
block 4 < -c(1,1,2,2)
block_6 <- c(1,1,1,2,2,2)
theseed = 42
set.seed(theseed)
site loop <- foreach (si = site hold, .combine=rbind) %do% {</pre>
  site num <- si
  strata loop <- foreach (s = strata hold, .combine=rbind) %do% {</pre>
    strata num <- s
    full block <- foreach (i =1:5, .combine=rbind) %do% {</pre>
      get random block <- rbinom(1, 1, 0.5)</pre>
      if (get random block == 1) {
        block <- sample(block 6, 6, replace = FALSE)
      if (get random block == 0) {
        block <- sample(block 4, 4, replace = FALSE)</pre>
      full block <- as.matrix(block)</pre>

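### The septic shock objective has no pre-specified definition or analysis, and its nearest proxy subgroup rests on two conflicting cardiovascular SOFA tables

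*Protocol*

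**What the plan says.** Protocol Section 2.2 and the synopsis both list the secondary objective "To demonstrate the efficacy of AB103 in patients with septic shock". The protocol mentions septic shock again in the corticosteroid note (5.2.1) and in the list of expected adverse events (8.5.1), without defining it. It does not appear in the secondary measures (7.2), the secondary analyses (9.2.4) or the exploratory subgroups (9.2.5).

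The SAP does not use the term. Its secondary endpoints (4.1 to 4.3, 5.7), subgroup list (4.6) and table list (Appendix 1) contain no septic shock analysis. SAP 1 states that the SAP takes precedence where the two documents differ. SAP 1.1 describes the version 4.0 changes as two types, AKI endpoints and needs of the marketing application, and says nothing about dropping this objective.

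The nearest item is subgroup 7 in SAP 4.6: "Presence of cardiovascular organ failure (SOFA component >=3 at baseline) vs. those without CV organ failure". SAP 5.1 uses the same cut to describe baseline sepsis, as "reflected in screening component SOFA scores of 3 or 4" for the cardiovascular and respiratory components.

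For scoring, SAP 3.5.4 says that the modified SOFA "will be calculated as described in Section 5.2 and Appendix 5". In SAP Appendix 5 the cardiovascular score of 4 reads "Dopamine > 15 OR epinephrine > 0.1 OR norepinephrine > 0.1", and no row mentions phenylephrine or vasopressin. In protocol Appendix C the corresponding cell reads "Dopa>15 Epi>0.1 NE>0.1 PE>300 VP>0.01", with a footnote that "phenylephrine (PE) is micrograms/min; vasopressin (VP) is U/min".

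**The concern.** A declared objective with no definition or named analysis yields no result labelled as its answer. If a definition of shock is first chosen after unblinding, it is post hoc and open to selection.

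The obvious substitute, subgroup 7, has its own problem. The same patient can fall on either side of the cut depending on which document's table is used. If patients whose pressure is held by vasopressin or phenylephrine alone are counted as free of cardiovascular failure, shocked patients are mixed into the comparison stratum, and any difference in effect by shock status is blurred.

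The conflict is not confined to this subgroup. The cardiovascular component enters every mSOFA total, including the Day 14 score within NICCE.

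**Working it through.** **Step 1. The plan's own figure.** The documents give no figure for septic shock. The whole-trial power does reproduce. For a pooled chi-square test,

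power = Φ{[Δ − z√(2p̄q̄/n)] / √[(p₁q₁ + p₂q₂)/n]}.

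With n = 145 per arm, 0.60 vs 0.40 and two-sided α = 0.01 (z = 2.576):
- √(0.50/145) = 0.0587, so z times this is 0.151
- √(0.48/145) = 0.0575
- power = Φ[(0.200 − 0.151)/0.0575] = 80.2%, as stated in protocol 9.1.2 and SAP 2.4.1

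**Step 2. The two cardiovascular tables side by side.** Each row is a patient on one agent only. Where the agent has no entry, the score is 0 if MAP is at least 70 and 1 if below. The doses are test inputs for the tables, and Appendix C's one-hour administration condition is taken as met.

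| Agent alone | SAP Appendix 5 | Protocol Appendix C | Subgroup 7 (SAP / protocol) |
|---|---|---|---|
| Vasopressin 0.03 U/min | 0 or 1 | 4 | without / **with** |
| Vasopressin 0.01 U/min | 0 or 1 | 0 or 1 (no entry) | without / without |
| Phenylephrine 50 µg/min | 0 or 1 | 2 | without / without |
| Phenylephrine 200 µg/min | 0 or 1 | 3 | without / **with** |
| Phenylephrine 350 µg/min | 0 or 1 | 4 | without / **with** |
| Norepinephrine 0.05 µg/kg/min | 3 | 3 | with / with |
| Dopamine 4 µg/kg/min | 2 | 2 | without / without |
| Dobutamine | 2 | 0 or 1 (no entry) | without / without |

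Three rows change sides. The one-hour condition is also absent from SAP Appendix 5.

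**Step 3. Which table governs subgroup 7.** The evidence points both ways.
- For Appendix 5: SAP 3.5 and 3.5.4 name it as the source of the computations, and the SAP takes precedence.
- For the recorded score: under protocol 6.2.8 site personnel calculate the screening mSOFA, and the protocol's modified SOFA table is Appendix C. SAP 5.2 item 5 adjusts a recorded screening mSOFA by removing certain GCS scores, which implies that the site value is the starting point.

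Neither document settles the matter.

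**Step 4. What a shock subgroup could deliver.** The share in shock is not given; 20% to 60% is assumed. With n = 145f per arm, 0.60 vs 0.40, nominal two-sided α = 0.05, and 95% half-width = 1.96√(0.48/n):

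| Share f | n per arm | Half-width | Power |
|---|---|---|---|
| 0.2 | 29.0 | 1.96√(0.48/29) = 0.25 | 33% |
| 0.3 | 43.5 | 0.21 | 46% |
| 0.4 | 58.0 | 0.18 | 58% |
| 0.5 | 72.5 | 0.16 | 68% |
| 0.6 | 87.0 | 1.96√(0.48/87) = 0.15 | 76% |

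**Step 5. Illustration of misplacement.** Suppose a fraction m of shocked patients is moved to the side without failure (assumed 5% to 30%), with the effect in those remaining unchanged. Then n per arm = 145f(1 − m), and the shocked share of the other group is fm/(1 − f + fm).
- f = 0.3: power falls from 46% to between 44% and 34%; shocked share 2.1% to 11.4%.
- f = 0.5: power falls from 68% to between 65% and 52%; shocked share 4.8% to 23.1%.

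**The case against.** The strongest reply is that most of what the objective needs is already planned under another name. For subgroup 7 the SAP repeats, by arm, the NICCE table with its components (which include Day 28 survival), the CCPE table, and the critical care, debridement, renal and adverse event tables. Figures 47 and 48 give forest plots with 95% intervals. SAP 5.5 allows treatment interactions as needed. This stands. A reader might infer that the objective cannot be answered at all; the documents do not support that. What is missing is a definition and a stated link from objective to analysis.

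The second reply is that misplacement is conditional, and this also stands. A reader might infer that patients on vasopressin or phenylephrine alone will be misclassified. If the site-recorded component was scored on protocol Appendix C, vasopressin above 0.01 and phenylephrine from 100 fall on the side with failure. SAP Appendix 5 is also headed as the full SOFA, range 0 to 24 with liver, so it may not have been meant to replace the protocol's modified table. None of this removes the conflict: the SAP still names Appendix 5 for the modified score.

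The third reply is that lack of error control is not special to this objective. Other secondary objectives are also phrased as demonstrations, secondary analyses are declared generally descriptive (SAP 5.7), type 1 error is openly uncontrolled beyond the key secondary endpoint (SAP 5.6), and subgroups are supportive or hypothesis-generating (SAP 5.5). That is a disclosed choice, so rewording the objective is largely editorial.

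**Conclusion.** The point holds in this form: the septic shock objective has no pre-specified definition or analysis in either document, and the nearest proxy is exploratory and depends on two cardiovascular tables that disagree for vasopressin above 0.01 U/min and phenylephrine from 100 µg/min. Under the SAP table, patients on either agent alone score 0 or 1; under the protocol table they score 3 or 4 at those levels.

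The size of any misplacement is unknown. The documents give neither the share of patients in shock nor the share on these agents alone, and do not say which score feeds the subgroup. The power figures in Step 4 should not be read as the harm done: they describe a subgroup of assumed size and would apply with a perfect definition. They show only that, at an assumed share of 30% to 50%, such a subgroup supports estimation to about ±0.21 to ±0.16 on the NICCE difference, not a demonstration. Step 5 is an illustration on assumed fractions.

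The missing septic shock analysis does not invalidate the primary, co-primary or key secondary tests. The table conflict reaches every mSOFA score and needs resolving for that reason too.

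**What to change.** Before unblinding:

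1. Reconcile SAP Appendix 5 with protocol Appendix C, so that one cardiovascular table covering all the listed vasopressors is used for every mSOFA use. State that subgroup 7 uses it, and whether the baseline component is the site-recorded value or a re-derived one.
2. In SAP 4.6, name the baseline shock subgroup that answers the objective. This can be subgroup 7 on the reconciled table, or a flag defined by the sponsor from the vasopressor data already collected from screening. The documents contain no definition of septic shock, so the choice is the sponsor's. Reconciliation alone would leave some vasopressor-treated patients below the cut, such as those on phenylephrine under 100 or dopamine up to 5, and the sponsor should say whether that is intended.
3. Report NICCE, CCPE and Day 28 survival by arm within each level in the mITT set, with 95% intervals and a treatment-by-subgroup interaction, labelled as estimation and not confirmatory. Word the objective to match. If the objective is no longer intended, say so in the SAP.

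The cost is one reconciled table, one more subgroup run in existing tables and forest plots, and a less strongly worded objective. No new data collection is planned for this; a re-derived component would need the agent and dose behind each recorded mSOFA, which the sponsor should confirm are held.
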